Perioperative Virtual Reality for Pediatric Anesthesia

ClinicalTrials.gov Identifier: NCT03583450

Date approved: August 22, 2018

Protocol and Statistical Analysis

In this pragmatic, randomized controlled, parallel-group study, children aged 5 to 12 years scheduled for elective surgery with general anesthesia are randomly allocated to a virtual reality group (VR group) or a non-virtual reality control group (No VR group). Parental written informed consent and, for children aged 7 years or greater, pediatric assent are obtained prior to enrollment. Following baseline measurement, participants are randomized using a secure, web-based application and the aid of a statistician. The simple randomization sequence is concealed from study staff until completion of baseline assessment. Patients in the VR group receive audiovisual distraction with a VR headset during inhaled mask induction of general anesthesia in the operating room. The No VR group serves as the control group and receives standard medical care without any audiovisual devices.

Patients assigned to the VR group receive a customized Samsung Gear VR headset that displays a pre-selected, interactive game designed for pediatric perioperative use featuring an animated animal character moving through a landscape. In the preoperative area, patients in the VR group receive a five-minute orientation to the headset that includes instructions, an opportunity to temporarily wear the headset, adjust headset fit to the patient, and operate the controller. The VR headsets are then administered immediately before induction of GA. The headsets are non-disposable and cleaned between uses with disposable antimicrobial wipes.

Anesthesia providers conduct routine anesthetic care at their medical discretion independent of VR use, including the use of pre-medication for anxiolysis or parental presence during induction. The standard inhaled mask induction of general anesthesia

consists of using an age appropriate mask and circle system to administer oxygen (3 L/min) and nitrous oxide (7 L/min) for approximately one minute followed by an incremental increase in sevoflurane to a maximum vaporizer setting of 8%. An intravenous catheter is placed after inhaled induction of anesthesia and the elective surgery or procedure is performed.

The primary outcome is preoperative pediatric anxiety as measured by the Modified Yale Preoperative Anxiety Scale (mYPAS). The mYPAS is administered at three time points: in the preoperative holding area (baseline, or T0), on entering the operating room (T1), and during induction of general anesthesia (T2). An independent anesthesiologist who is not part of the anesthesia team delivering care records all measurements. Secondary outcomes are perioperative parental anxiety, pediatric induction compliance, and parental and patient satisfaction. Perioperative parental anxiety is measured using the State-Trait Anxiety Inventory (STAI) at two time points: in the preoperative holding area (baseline, or T0) and after induction of general anesthesia (T3). Pediatric induction compliance is measured by the Induction Compliance Checklist (ICC) during induction of general anesthesia (T2). Parental and patient satisfaction with the perioperative experience is measured with a previously reported 21-item parental and patient satisfaction questionnaire after induction of general anesthesia (T3).

For analysis, data is visualized using histograms and the Shapiro-Wilk test is used to determine whether continuous data are normally distributed. The Wilcoxon rank sum test is used for univariate comparisons for all continuous and ordinal data between the VR and No VR groups, and Fisher's exact test is used to compare categorical data. The mYPAS score has three repeated measurements over time (T0, T1, and T2) and

the between-group effect for the use of VR. The primary analysis is a univariate comparison of mYPAS scores from T0 to T1 and T0 to T2 using Wilcoxon rank sum tests. The effect size corresponding to the primary analysis is the difference in medians, with the confidence limits calculated by bootstrapping with replacement with 200,000 repetitions. The mYPAS scores are also modeled using linear mixed-effects regression to address the within-subject correlation of mYPAS scores and the two repeated-measures time points (T1 and T2). The model incorporates random slopes (i.e., trend over time from T1 to T2) and intercepts for each patient, and adjusts for baseline mYPAS score (T0), which is obtained prior to randomization.

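### Two between-group Wilcoxon tests (T0 to T1 and T0 to T2) are jointly primary, with no alpha, success rule, order or multiplicity control

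*Combined protocol and SAP*

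**What the plan says.** All references are to the single section headed Protocol and Statistical Analysis.

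- **Outcome.** "The primary outcome is preoperative pediatric anxiety as measured by the Modified Yale Preoperative Anxiety Scale (mYPAS)". Three measurement times are listed: baseline in the holding area (T0), then "on entering the operating room (T1), and during induction of general anesthesia (T2)". None is named as the primary time point.
- **Primary analysis.** "The primary analysis is a univariate comparison of mYPAS scores from T0 to T1 and T0 to T2 using Wilcoxon rank sum tests".
- **Type of comparison.** The same paragraph makes these tests between arms: "The Wilcoxon rank sum test is used for univariate comparisons for all continuous and ordinal data between the VR and No VR groups".
- **Effect size.** "The effect size corresponding to the primary analysis is the difference in medians, with the confidence limits calculated by bootstrapping with replacement with 200,000 repetitions". No confidence level is given.
- **Mixed model.** "The mYPAS scores are also modeled using linear mixed-effects regression". The word *also*, coming after the primary analysis has been named, makes this a further analysis.
- **Timing of the intervention.** "Patients in the VR group receive audiovisual distraction with a VR headset during inhaled mask induction of general anesthesia in the operating room". The design description adds that the headset is put on just before induction.

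The text contains no alpha, sidedness, either-or-both rule, testing order or multiplicity adjustment.

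**The concern.** With two tests in the primary analysis, the error rate of the primary conclusion depends on how they are combined, and the plan leaves that open. Suppose one comparison is significant and the other is not. The trial could then be read as positive or negative, and the choice would be made with the results in view.

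Such a split result is plausible here. T1 is entry to the operating room, and T2 is induction, when the distraction is delivered. An effect at T2 without one at T1 is therefore easy to imagine. An either-test reading would claim success at more than the nominal error rate. A both-tests reading would hold the error but would let a miss at T1 cancel a clear effect at T2.

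A smaller gap is that the plan does not say outright which quantity is ranked. The phrase about comparing from T0 to each later time suggests the change from baseline.

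**Working it through.** The plan states no alpha, power or sample size, so there is no figure of its own to reproduce.

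**Inputs**
- From the document: two primary comparisons, between-group rank sum tests, measurements on the same children.
- Assumed: two-sided 0.05 per test (critical value 1.96), no effect at either time, and correlation r between the two test statistics.

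**Either-test rule.** Family-wise error = 1 − P(|Z1| < 1.96 and |Z2| < 1.96), with (Z1, Z2) standard bivariate normal.

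**Both-tests rule, no effect at either time.** P(both reject) = 0.05 + 0.05 − (either-test error).

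| r | P(neither rejects) | Either-test error | P(both reject) |
|---|---|---|---|
| 0 | 0.9025 | 9.75% | 0.25% |
| 0.5 | 0.9093 | 9.07% | 0.93% |
| 0.6 | 0.9125 | 8.75% | 1.25% |
| 0.8 | 0.9219 | 7.81% | 2.19% |
| 0.9 | 0.9296 | 7.04% | 2.96% |
| 0.99 | 0.9434 | 5.66% | 4.34% |

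At r = 0 the first figure is 0.95² = 0.9025. The sign of r is irrelevant for two-sided tests, so 9.75% is the maximum, and the error stays above 5% for any r short of 1. Under a both-tests rule the error is at most 5% even if only one time point has a true effect, because the other test must still reject falsely.

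**Plausible values of r.** With equal variances, the correlation of the two changes from baseline is

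(r12 − r01 − r02 + 1) / √[(2 − 2·r01)(2 − 2·r02)],

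where r01, r02 and r12 are the score correlations for T0–T1, T0–T2 and T1–T2. The document gives no values. Four assumed patterns:

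| r01, r02, r12 | Correlation of changes | Either-test error |
|---|---|---|
| 0.5, 0.5, 0.5 | 0.50 | 9.07% |
| 0.5, 0.3, 0.5 | 0.59 | 8.78% |
| 0.3, 0.3, 0.7 | 0.79 | 7.89% |
| 0.5, 0.5, 0.8 | 0.80 | 7.81% |

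**Check with Wilcoxon tests.** The simulation used 40,000 null trials in each of 24 settings: 20, 35 or 60 per arm (assumed), the four patterns above, and normal or skewed stepped scores with a floor.
- Either-test error, changes from T0 ranked: 7.7–9.1%.
- Either-test error, T1 and T2 scores ranked: 7.7–9.2%.
- T2 first, then T1 only if T2 is significant (changes): 4.8–5.2%, which is 5% within simulation error.

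The finding therefore does not depend on sample size or on which quantity is ranked.

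**Power under rules that control the error.** Start from an assumed 80% power at T2 with two-sided 0.05, so the mean of Z2 is 1.960 + 0.842 = 2.802.
- Equal alpha split (0.025 each, critical value 2.241): Φ(2.802 − 2.241) = Φ(0.560) = 71%.
- Both tests required: 69% (r = 0.5) to 73% (r = 0.8) if T1 also has 80% power; 46% to 49% if T1 has 50%.
- Hochberg's procedure: about 77% at each time if both have 80% power; 73–74% at T2 if T1 has 50%.
- T2-first fixed sequence: 80% at T2. T1 can be claimed only when both reject, so its power is 69–73% if each test alone has 80%.

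**The case against.** The strongest reply is that the plan never speaks of success or claims. It names one outcome and pairs the comparisons with an effect size and confidence limits, so both time points might simply be reported with their intervals. In that light the 9.1% to 7.0% range is not a property of the plan. It needs an assumed alpha, an assumed either-test rule and an assumed correlation, and the 0.9 end lies beyond the four patterns tried, which stop at 0.80 (7.8%). This stands as a limit on the number, which is conditional. It does not remove the gap: the plan specifies significance tests, calls them primary and does not say how they combine.

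The available text is also damaged. The sentence just before the primary-analysis sentence is broken in extraction, so a rule lost there cannot be strictly excluded. The break falls in a sentence introducing the repeated measurements, and the complete sentences that follow contain no such rule, so a lost rule is unlikely.

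Finally, testing T2 first is a choice. The plan treats the two times alike, and children in the VR arm have a five-minute headset orientation before surgery, so an effect on entry to the operating room is conceivable. Hochberg's procedure needs no ranking of the times. If both have 80% power it serves T1 better (about 77% against 69–73%) and T2 slightly worse (about 77% against 80%). That is a fair alternative for a sponsor who values both times equally. It does not make the fixed sequence unsound, and the timing of the intervention supports putting T2 first.

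**Conclusion.** The concern holds. Two between-group tests are jointly primary and no rule connects them, so the type I error of the primary conclusion is undefined. If the either-test rule applies, the error is 9.1% at r = 0.5 and 7.0% at r = 0.9, and at most 9.75%, given two-sided 0.05 per test and no effect at either time. That is an excess of at most 9.75 − 5 = 4.75 percentage points. Under a both-tests rule there is no excess, at a cost in power. The design itself is not invalidated, but the rule should be fixed before any comparison by arm is seen.

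**What to change.** State in the analysis paragraph:

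1. The single primary test is the between-group Wilcoxon rank sum comparison of the change in mYPAS from T0 to T2, at two-sided 0.05.
2. The change from T0 to T1 is tested in the same way, at two-sided 0.05, only if the first test is significant.
3. The ranked quantity is the change from T0. The planned difference in medians with bootstrap limits is reported for both comparisons whatever the test results.

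This holds the family-wise error at 5% with no alpha split. It needs two or three sentences and leaves the test, data collection and sample size as they are. The price is that no claim can be made at T1 if T2 fails. If the sponsor regards the two times as equally important, Hochberg's procedure or an explicit both-tests rule would also close the gap, with the power costs shown above.

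### The deciding mYPAS test uses baseline by subtraction at most, and STAI has no named baseline-adjusted analysis: valid tests, but a possible loss of precision

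*Combined protocol and SAP*

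**What the plan says.** All the relevant text is in the single unnumbered section of the combined protocol and SAP (Protocol and Statistical Analysis).

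- **Primary test:** "The primary analysis is a univariate comparison of mYPAS scores from T0 to T1 and T0 to T2 using Wilcoxon rank sum tests". The sentence does not say whether differences from T0 or the raw T1 and T2 scores are ranked.
- **Effect size:** "The effect size corresponding to the primary analysis is the difference in medians", "with the confidence limits calculated by bootstrapping with replacement with 200,000 repetitions".
- **Mixed model:** "The mYPAS scores are also modeled using linear mixed-effects regression". It covers T1 and T2, has random slopes and intercepts per patient, and "adjusts for baseline mYPAS score (T0), which is obtained prior to randomization".
- **General rule:** "The Wilcoxon rank sum test is used for univariate comparisons for all continuous and ordinal data between the VR and No VR groups".
- **STAI:** "Perioperative parental anxiety is measured using the State-Trait Anxiety Inventory (STAI) at two time points", namely T0 in the holding area and T3 after induction. No STAI-specific analysis is given, so only the general rule applies.
- **Order of events:** "Following baseline measurement, participants are randomized using a secure, web-based application". The allocation sequence stays hidden from study staff until baseline assessment is finished.

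**The concern.** A baseline score of the outcome itself is often its best predictor, and here it is collected for both anxiety scales before allocation. It is therefore a legitimate covariate, and the plan treats it as one in the mixed model. The test that decides the trial has no covariate. Subtracting T0 fixes the slope of follow-up on baseline at 1, whatever the data show. Ranking raw follow-up scores fixes it at 0. Either choice can leave explainable variation in the comparison.

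What is at stake is power for the primary outcome and for parental anxiety, using data the trial already holds. For STAI the gap is fuller, because not even a supporting adjusted analysis is named.

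**Working it through.** **Inputs.** The documents give no sample size, significance level, target difference, SD or baseline to follow-up correlation, so there is no stated figure to reproduce. Everything below is assumed: 50 per arm, two-sided 5%, normal scores, r = 0.3, 0.5 or 0.7, and k = follow-up SD / baseline SD from 0.75 to 2.

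**Shift.** It is reset at each r so that linear ANCOVA has about 80% power. In follow-up SDs, shift = (1.960 + 0.842) × √(2/50) × √(1 − r²) = 0.560 × √(1 − r²), which is 0.535 / 0.485 / 0.400. The effect therefore shrinks as r rises. The tables compare tests at a given r; they do not show that any one test loses power as r rises.

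**Simulated power (%), r = 0.3 / 0.5 / 0.7, 10,000 trials per case.**

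| k | Wilcoxon on change | Rank ANCOVA | Gain (points) |
|---|---|---|---|
| 0.75 | 44.2 / 50.4 / 51.7 | 76.5 / 76.3 / 74.9 | +32 / +26 / +23 |
| 1 | 58.8 / 64.4 / 70.2 | 76.5 / 75.3 / 74.5 | +18 / +11 / +4 |
| 1.5 | 72.7 / 76.8 / 76.7 | 77.0 / 76.6 / 74.1 | +4 / 0 / −3 |
| 2 | 76.1 / 76.8 / 73.3 | 76.9 / 75.5 / 74.6 | +1 / −1 / +1 |

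Allowing for simulation error, the range at k = 1.5 to 2 is about +5 to −3.

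**If raw follow-up scores are ranked.** Wilcoxon power is 73.4 / 65.0 / 49.2, against 76.5 / 75.3 / 74.5 for rank ANCOVA. The differences are 3.1 / 10.3 / 25.3, or 4 / 10 / 26 from whole percentages (77 − 73, 75 − 65, 75 − 49). They do not depend on k, because neither test changes when follow-up is rescaled.

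**Hand check.** For normal data, Wilcoxon power is about Φ(shift/σ × √(50/2) × √(3/π) − 1.960), with √(3/π) = 0.977.

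- Raw scores, r = 0.7: 0.400 × 5 × 0.977 = 1.95, so Φ(−0.01) is about 50% (simulated 49.2%).
- Change, k = 1, r = 0.5 (σ = 1): 0.485 × 5 × 0.977 = 2.37, so Φ(0.41) is about 66% (simulated 64.4%).

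**Why the gain disappears.** The variance of change relative to linear ANCOVA is (1 + k² − 2rk) / (k²(1 − r²)). Its excess over 1 is (1 − rk)² / (k²(1 − r²)), which is zero at rk = 1. At k = 2, r = 0.5 it is 3 / (4 × 0.75) = 1. Subtraction costs nothing when the true slope happens to be 1.

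**STAI.** The planned test is again Wilcoxon, so the rank-test figures above apply: the raw-score comparison if T3 alone is ranked, the table if change is ranked. Sample-size formulas for linear ANCOVA do not describe this comparison.

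**Validity.** At 63 per arm, the simulated type I error of the two Wilcoxon tests was 4.5% to 5.4%, for normal and for skewed data with a floor. For rank ANCOVA at 50 per arm it was 4.4% to 5.4%.

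**Skewed or floored scores (illustrative only).** With lognormal scores at k = 1, change-score power was 49.5 / 55.6 / 62.0 with the shift in one direction and 60 / 65 / 69 in the other. On assumed floored scales at latent k = 1, the gain ran from +24 / +18 / +11 (19% at the floor at both times) to +5 / +2 / 0 (55% at baseline, 8% at follow-up).

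**Mixed model.** A random intercept and slope need two variances and a covariance; residual error adds a fourth parameter. The covariance matrix of T1 and T2 has three distinct elements. Four parameters cannot be separated from three.

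**The case against.** The best case for the plan is that a rank test paired with a difference in medians is simple, suits scores that may not be normal, and reports in mYPAS points. A T0-adjusted mYPAS analysis is already pre-specified, so for that outcome the dispute is only over which analysis decides. T2 is taken during induction, where anxiety may well spread more than in the holding area. If so, k exceeds 1 and the gain over change scores is small or nil. All of this stands, and it limits the weight of the point. It does not reach STAI, where no adjusted analysis is named, or the raw-score reading, where the loss does not depend on k.

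Three stronger inferences are tempting, and the documents support none of them.

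- **That the unadjusted tests are biased or invalid.** Baseline precedes a concealed random allocation, so each test holds its level.
- **That the plan ignores baseline for mYPAS.** The mixed model adjusts for it.
- **That a large loss of power is established.** r, k and N are all absent, and some plausible settings show no loss.

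Nor should the mixed model simply be promoted to primary. As written, its random-effects structure cannot be identified from two outcome times.

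**Conclusion.** The point holds as one of efficiency, not error. The deciding mYPAS test uses T0 by subtraction or not at all, and STAI has no named adjusted analysis.

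Under the stated assumptions, the possible gain from adjustment runs from worthwhile (change scores with similar spread at both times and modest correlation, or raw scores with high correlation) to nil or 2 to 3 points negative (change scores with follow-up much more variable than baseline and strongly correlated with it). The k = 0.75 row shows how far the range extends, but the conclusion does not rest on it. Nor does it rest on the skewed or floored results, which move with the simulation choices.

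Severity is optional to moderate. The case is firmest for STAI.

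**What to change.** 1. **STAI.** Compare STAI at T3 between groups by rank ANCOVA (ranks of T3 adjusted for ranks of T0).
2. **mYPAS.** Test at T1 and at T2 by rank ANCOVA (ranks of follow-up adjusted for ranks of T0). Keep the planned difference in medians with bootstrap limits as the required effect size, because a rank-ANCOVA coefficient is not in mYPAS points. Report the planned Wilcoxon test as a sensitivity analysis, and state whether it ranks change or raw scores. A T0-adjusted median difference from median regression is optional and should be labelled as conditional on T0.
3. **Mixed model.** Keep it, T0-adjusted, as a supporting analysis, with an unstructured 2 × 2 covariance for T1 and T2 or a random intercept only.

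The cost is SAP wording and a little code, with no new data. The change should be made before outcomes are seen by group.

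There are two downsides. The interval for the raw difference in medians may at times disagree with the adjusted p-value. I have no figure for that pairing, but the planned Wilcoxon and raw-median pair already disagreed in 9% to 23% of simulated trials, and rank ANCOVA with the optional adjusted median in 11% to 24%. The second is that power may not improve, or may fall by 2 to 3 points, in the setting named in the verdict.

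### Supporting mixed model: a random intercept plus random T1-to-T2 slope does not suit two outcomes per child. It is unidentified if the effects are correlated and restricts the variances if they are independent

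*Combined protocol and SAP*

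**What the plan says.** All of this is in the analysis text of the combined protocol and SAP, which has no numbered sections.

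- Purpose of the model: "The mYPAS scores are also modeled using linear mixed-effects regression to address the within-subject correlation of mYPAS scores". The same sentence limits the repeated measures to T1 and T2.
- Random effects: "The model incorporates random slopes (i.e., trend over time from T1 to T2) and intercepts for each patient".
- Role of baseline: the model "adjusts for baseline mYPAS score (T0), which is obtained prior to randomization". T0 is therefore a covariate and not a third outcome.
- Status: the model is supporting. "The primary analysis is a univariate comparison of mYPAS scores from T0 to T1 and T0 to T2 using Wilcoxon rank sum tests".

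The schedule has one mYPAS score at each time point, and no replicate at T1 or T2 is described. The plan does not give the covariance between intercept and slope, the time coding, any constraint on the residual variance, or a fallback if the model cannot be fitted. The sentence that introduces the time and group effects is broken in the available text.

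**The concern.** A random intercept and slope describe individual trajectories and need enough occasions to separate a child's own trend from measurement noise. With one score at each of two occasions, the change from T1 to T2 mixes the two. The model then has either more variance parameters than the data can support or, if intercept and slope are taken as independent, a restriction on the T1 and T2 variances that nobody chose on purpose.

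Two things are at stake. First, if the software refuses the fit, a replacement structure would be picked after the data are in hand. Second, under the independent form, the SEs of separate T1 and T2 contrasts can be wrong in opposite directions. T2 matters most here because it falls at induction, and "The VR headsets are then administered immediately before induction of GA".

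**Working it through.** **Inputs.** From the analysis text: two outcomes per child, two random effects per child, T0 as covariate. The documents give no variances, correlation or sample size for this model, so every variance value below is an assumption. The plan has no figure of its own to reproduce.

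**Notation.** V11, V22 and V12 are the variances and covariance of T1 and T2 given the fixed effects. Let a = intercept variance, b = slope variance, c = their covariance, s = residual variance, and k = V22/V11.

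**1. Correlated effects.** With 0/1 coding:

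- V11 = a + s
- V12 = a + c
- V22 = a + 2c + b + s

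Four unknowns face three equations. The Jacobian has rank 3 for codings 0/1, 1/2 and -0.5/+0.5. As an example, take V11 = 300, V22 = 350, V12 = 150. The sets (a, c, b, s) = (290, -140, 330, 10), (250, -100, 250, 50), (200, -50, 150, 100) and (150, 0, 50, 150) all reproduce it exactly. The slope variance can be anything from 50 to 330 across these sets with no change in likelihood. The fixed effects depend on the components only through V, so the VR estimate and its SE are the same for all four.

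**2. Independent effects (c = 0).**

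- 0/1 coding: V22 - V11 = b, which cannot be negative.
- 1/2 coding: V22 - V11 = 3b, which cannot be negative.
- -0.5/+0.5 coding: V11 = V22 = a + b/4 + s and V12 = a - b/4. The variances are forced equal, and three unknowns face two distinct equations (rank 2).

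**3. Independent effects, separate T1 and T2 contrasts, T2 less variable (k < 1).** The slope variance goes to zero and both fitted variances become (V11 + V22)/2. The ratio of model SE to true SE is sqrt((1+k)/(2k)) at T2 and sqrt((1+k)/2) at T1. With a two-sided 5% test and 80% true power, T2 power = Phi(2.8016 - 1.96 x ratio) and T1 type I error = 2[1 - Phi(1.96 x ratio)].

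| k | T2 SE ratio | T2 power | T1 SE ratio | T1 type I error |
|---|---|---|---|---|
| 0.8 | 1.061 | 76.5% | 0.949 | 6.3% |
| 0.67 | 1.116 | 73.0% | 0.914 | 7.3% |
| 0.5 | 1.225 | 65.6% | 0.866 | 9.0% |

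A REML simulation agrees in direction and size (0/1 coding, T0-adjusted, correlation 0.5, 1,500 trials of an assumed 70 children). In order of k, T1 type I error was 6.3%, 8.0%, 10.5%, against 4.8%, 5.9%, 5.5% with an unstructured covariance. T2 power was 75.0%, 72.3%, 63.2%, against 78.4%, 79.5%, 79.0%.

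**4. Independent effects, T2 more variable (k > 1).** Set V11 = 1. There is no SE error only if the solved components are non-negative.

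- 0/1 coding: a = V12 and s = V11 - V12, so 0 <= V12 <= 1 is needed.
- 1/2 coding: a = V12 - (2/3)(V22 - V11), so V12 >= (2/3)(k - 1) is needed, together with s = V11 - V12 + (V22 - V11)/3 >= 0.

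The cases are:

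- Correlation 0.5, k = 1.25, 1.5, 2: V12 = 0.559, 0.612, 0.707. All are below 1 and above 0.167, 0.333, 0.667, and s is positive. No error under either coding.
- Correlation 0.3, k = 2, 1/2 coding: V12 = 0.424 < 0.667, so a sits at zero. Then s = (4 - 4 x 0.4243 + 2)/5 = 0.8606, 5b + s = (1 + 4 x 0.4243 + 8)/5 = 2.1394, and b = 0.2558. Fitted variances are s + b = 1.116 and s + 4b = 1.8837. SE ratios are sqrt(1.116) = 1.057 at T1 and sqrt(1.8837/2) = 0.970 at T2.
- Correlation 0.8, k = 2, 0/1 coding: V12 = 1.131 > 1, so s sits at zero. Then a = 1 and b = 1 + 2 - 2 x 1.131 = 0.737. The fitted T2 variance is 1.737, and its SE ratio is sqrt(1.737/2) = 0.932. T1 is unaffected.

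Under -0.5/+0.5 coding the step 3 formulas apply for k > 1 too. At k = 1.25, 1.5, 2 the T2 SE is 5%, 9%, 13% too small and the T1 SE 6%, 12%, 22% too large.

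**The case against.** The strongest reply is that the correlated form does no inferential harm. It can reproduce any positive-definite 2x2 covariance, so it yields the same VR estimate and SE as the proposed replacement. The plan gives the model's purpose as handling within-child correlation and does not list the variance components as results to report. That stands. What is left under this form is a possible refusal by the software and components that cannot be interpreted.

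The SE errors under the independent form need conditions the documents do not state: independent effects, separate T1 and T2 contrasts, and variances that break the restriction. That stands too. The percentages are illustrations, and only the parameter counts and variance restrictions are certain.

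Two possible rescues fail on the text. Fixing the residual variance would restore identification, but no such constraint is stated. Treating T0 as a third outcome would give six covariance elements for four parameters, but the text makes T0 a covariate.

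A reader might also infer that the plan omits a group-by-time term, or that the model blurs T1 and T2 into one coefficient. The documents do not support this. The sentence on time and group effects is broken just before "the between-group effect for the use of VR", so the full fixed-effects list cannot be judged. A pooled coefficient would in any case average the two time points under an unstructured covariance as well, so it is not a fault of the random effects.

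**Conclusion.** The point holds as a minor one. As written, the random-effects structure is either unidentified or carries an unstated restriction on the T1 and T2 variances. That follows from the plan's own description, given a freely estimated residual variance, and needs no assumed values. The sizes in steps 3 and 4 do rest on assumed variance ratios and correlations, and apply only to independent effects with separate contrasts.

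Two stronger readings should be resisted. One is that the VR effect is biased or cannot be estimated: under correlated effects it and its SE are fully determined. The other is that the trial's main result is at risk: the primary Wilcoxon comparisons do not use this model. Equally, it would be wrong to conclude that the independent form is always safe when T2 is the more variable, since step 4 gives SE errors of about 3% to 7% in cases where the covariance does not fit non-negative components.

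**What to change.** In the supporting model, replace the random intercept and slope with an unstructured 2x2 within-child covariance for T1 and T2. It has three parameters, all identifiable, puts no restriction on the two variances, and still deals with within-child correlation. Keep the T0 adjustment and the planned fixed effects as they are. A random intercept alone would also be identified, but it assumes equal variances and so brings back SE errors for separate contrasts whenever T1 and T2 differ in variability.

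The cost is one line of SAP and code. No further data are needed, and the primary analysis does not change.
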